7.3 LOST TO FOLLOW-UP

A participant will be considered lost to follow-up if he or she fails to return for [specify number of visits] scheduled visits and study staff are unable to contact the participant after at least 3 attempts.

The following actions must be taken if a participant fails to return to the clinic for a required study visit:

- The site will attempt to contact the participant, reschedule the missed visit [specify time frame], counsel the participant on the importance of maintaining the assigned visit schedule and ascertain if the participant wishes to and/or should continue in the study
- Before a participant is deemed lost to follow-up, the investigator or designee will make every effort to
 regain contact with the participant (where possible, 3 telephone calls and, if necessary, a certified letter
 to the participant's last known mailing address or local equivalent methods). These contact attempts will
 be documented in the participant's medical record or study file.
- Should the participant continue to be unreachable, he or she will be considered to have withdrawn from the study with a primary reason of lost to follow-up

8 STUDY ASSESSMENTS AND PROCEDURES

8.1 ENDPOINT AND OTHER NON-SAFETY ASSESSMENTS

Demographic characteristics. Participants self-reported their demographics at baseline by taking an online survey through Qualtrics, Inc. The survey was filled out interview-style with research team members on their computers during enrollment. Participants reported their age, gender, race and ethnicity, education level, income, marital status, length of stay at the retirement community, and height (in.) and weight (lb.). Body-mass index (BMI) will be calculated using the formula weight (lb.) / [height (in.)]².

Aim 1: Physical activity. At the beginning of the study, participants were given a Fitbit Zip activity monitor to wear on the wrist for 12 weeks. The Fitbit Zip was asked to be worn on the wrist because evidence suggests accelerometers worn on at the hip have lower wear-time compliance. The Fitbit Zip is a small (35.6 x 28.9 x 9.6 mm) commercially-available triaxial accelerometer-based physical activity monitor that estimates steps taken per day. The Fitbit (One or Zip) worn on the hip has been demonstrated as a valid and reliable measure of average steps/day among community dwelling older adults compared to the ActiGraph GT3X+ (ICC=0.94, 95% CI 0.88 to 0.97) (Paul et al., 2015). Through the Fitbit application programming interface, the research team will be able to access each participant's physical activity data minute-by-minute each day the activity monitor is worn. Participants were instructed to wear the monitor during all waking hours (except time spent swimming or bathing) for thirteen consecutive weeks.

Aim 2: Psychosocial outcomes. This will be measured with the Self-Efficacy for Exercise (SEE) scale, a 13-item questionnaire designed to assess the participant's self-efficacy related to their ability to continue exercising in the face of barriers

Outcome expectations will be measured with the Outcome Expectations for Exercise (OEE) Scale. The OEE is a valid and reliable 9-item scale that assess the participant's outcome expectations and benefits associated with exercise.

Social isolation will be assessed with the Friendship Scale (FS). The FS is a 6-item scale that assesses six dimension contributing to social isolation.

Aim 3: Satisfaction and adherence. To assess the acceptability of the intervention, we will measure participant adherence and satisfaction. Acceptability is important to assess because we want to be able to determine if older adults thought MapTrek was a fun game for increasing physical activity. Specifically, we will be able to determine which intervention features they thought were helpful. Adherence will be measured by examining the enrollment, completion, and compliance rates. Enrollment rate will be assessed by documenting the number of people who enroll in the study from the number of people living in the retirement community, and completion rate will be assessed by the

number of people who finish the study out of those who enrolled. Compliance rates will be assessed by examining the percentage of participants who are wearing and syncing their Fitbit over the course of the intervention. Process evaluations were administered to participants via phone or in-person during the first week after the active intervention. The process evaluation was used to assess the participant's satisfaction with the game features. Participants were asked what they most liked about the game, what barriers prevented them from playing the game, and what improvements they would recommend. This information will be used when developing future intervention in which MapTrek is used to promote physical activity among an older adult population. Focus groups (6-8 participants) will be held the third week of the follow-up timepoint.

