9.4.4 SAFETY ANALYSES

9.4.5 BASELINE DESCRIPTIVE STATISTICS

Descriptive statistics (i.e., mean, SD, frequency) will be calculated for participant characteristic including age, sex, height, weight, and BMI, education, total annual household income, and length of residence at the retirement community.

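### The BMI formula in section 8.1 omits the factor of about 703 that converts lb/in² to kg/m²; only a baseline descriptor is affected (minor correction)

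*Combined protocol and SAP*

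**What the plan says.** Section 8.1 (Endpoint and other non-safety assessments) lists the demographic items that participants self-report at baseline. Among them are "length of stay at the retirement community, and height (in.) and weight (lb"), so the units of collection are inches and pounds. The next sentence defines the derived variable: "Body-mass index (BMI) will be calculated using the formula weight (lb.) / [height (in".)], squared. The sentence ends there.

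Section 9.4.5 (Baseline descriptive statistics) says that means, SDs and frequencies will be produced for "participant characteristic including age, sex, height, weight, and BMI", together with education, household income and length of residence.

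No other section gives a BMI formula, a unit conversion, a unit for BMI or a BMI value.

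**The concern.** The formula names its own units, pounds over inches squared, and is otherwise complete. It therefore reads as a rule to be programmed, not as a loose description of BMI. BMI is conventionally expressed in kg/m², and a ratio in lb/in² is not on that scale. This is the only derivation rule in the documents for a variable that section 9.4.5 says will be reported.

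What is at stake is the description of the sample. The study is a single-arm pilot (section 4.1) that enrols residents and employees of one facility (section 6.1.1). Readers will use the baseline table to judge to whom the results apply. A BMI row on the wrong scale cannot be set beside other populations until it is rescaled.

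**Working it through.** **Inputs from the documents (section 8.1).** Weight W in pounds; height H in inches; rule as written: W / H². The documents state no BMI value, so there is no figure of the plan's own to reproduce.

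**Inputs assumed.** The intended unit is kg/m² (the convention; the documents name no unit). The BMIs, heights and weights below are illustrations, not trial data.

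**Step 1: the missing factor.** With 1 lb = 0.45359237 kg and 1 in = 0.0254 m,

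BMI (kg/m²) = (0.45359237 × W) / (0.0254 × H)² = (0.45359237 / 0.0254²) × W / H² = 703.07 × W / H².

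The factor does not depend on any participant's height or weight.

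**Step 2: the rule as written, over a range of true BMI.** The literal result is the true BMI divided by 703.07.

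| Assumed true BMI (kg/m²) | Result of the formula as written |
|---|---|
| 18.5 | 0.026 |
| 22 | 0.031 |
| 27 | 0.038 |
| 30 | 0.043 |
| 35 | 0.050 |
| 40 | 0.057 |

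**Step 3: the same check from assumed heights and weights.**

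| Weight (lb) | Height (in) | W / H² as written | × 703.07 |
|---|---|---|---|
| 150 | 64 | 150/4,096 = 0.037 | 25.7 |
| 170 | 66 | 170/4,356 = 0.039 | 27.4 |
| 190 | 70 | 190/4,900 = 0.039 | 27.3 |

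**Step 4: effect on the planned summaries.** Multiplication by a constant scales the mean and the SD by that constant. Both would therefore be too small by a factor of 703.07. Frequencies behave differently. If BMI were tabulated by cut-offs on the kg/m² scale, values of 0.03 to 0.06 would put every participant in the lowest category. Section 9.4.5 does not say that BMI will be categorised, so this last effect is conditional.

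**Step 5: where else BMI is used.** It does not appear in the eligibility criteria (5.1, 5.2), the hypotheses (9.1), the sample size (9.2), the primary analysis (9.4.2) or the secondary analyses (9.4.3). The sub-group and exploratory headings (9.4.7, 9.4.9) have no content.

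**The case against.** The best case against raising this is that it changes nothing that the study sets out to learn. BMI is one of several baseline descriptors, and no estimate, test, power figure or eligibility decision depends on it. The error is a constant multiplier, so ranking, relative spread and correlations are untouched. Multiplying the mean and SD by 703 restores them, and individual height and weight are on record. A mean BMI near 0.04 would probably be noticed, and software or staff may apply the factor without being told. All of this stands. It settles the severity, but it does not make the written rule correct, and the documents nowhere say that the factor will be applied.

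It can also be said that the documents never name kg/m², so that the fault is an unstated unit as much as a wrong formula. That is fair, and the size given here rests on the conventional unit.

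A reader might go further and infer that every reported BMI will be about 0.04 where about 27 is correct, or that the description of the sample would be meaningless. The documents do not support either reading. They give no BMI of 27 and no BMI result, and literal values would vary with the participant, from about 0.026 to 0.057 over the assumed range. Section 9.4.5 plans summaries, and the heading for individual tabulation (9.4.8) is empty. The documents contain no derivation code, so they show what is written and not what will be done.

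**Conclusion.** The formula in section 8.1 is wrong as written for BMI in kg/m². Used literally, it makes the baseline mean and SD too small by a factor of 703.07, and it would misplace participants in any table of kg/m² categories. The factor is exact given the units stated in the plan and rests on one assumption, that BMI is meant in kg/m². The range of 0.026 to 0.057 rests on the further assumption of true BMIs from 18.5 to 40.

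The effect stops at the baseline table. Eligibility, power and the endpoint analyses are untouched, and the correct values can be recovered from data already collected. This is a minor correction.

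**What to change.** In section 8.1, replace the formula with BMI (kg/m²) = 703 × weight (lb) / [height (in)]², or state that weight and height are converted to kilograms and metres before the ratio is taken. Give the unit in either case. Rounding the factor to 703 changes a BMI by about 0.01% (0.07/703.07), which is immaterial.

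Use the same rule, with the unit shown, for the BMI row of the section 9.4.5 table, and check that whatever program or spreadsheet derives the variable agrees with it. If BMI is to be shown as frequencies, state the categories.

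The cost is one constant and one unit in one sentence. No new data are needed, and nothing changes for participants or for study conduct.

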3 OBJECTIVES AND ENDPOINTS

OBJECTIVES	ENDPOINTS	JUSTIFICATION FOR ENDPOINTS	PUTATIVE MECHANISMS OF ACTION
Primary			
1. To determine the efficacy of MapTrek for improving physical activity levels of older adults living in a residential facility.	Assessments made at baseline, 8 weeks and 12 weeks.	We will determine whether the intervention was effective at 8 weeks and whether participants maintained outcomes at 12 weeks.	
Secondary			
1. To determine the efficacy of MapTrek for improving psychosocial outcomes(e.g., self-efficacy, social support, outcome expectations) among older adults living in a residential facility.		We will determine whether the intervention was effective at 8 weeks and whether participants maintained outcomes at 12 weeks.	
2. To determine the acceptability of MapTrek among older adults living in a residential facility.	We will assess acceptability at 8 weeks.	Participants will have just finished the intervention at 8 weeks.	
Tertiary/Exploratory			

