7.1 DISCONTINUATION OF STUDY INTERVENTION/EXPERIMENTAL MANIPULATION

When a subject discontinues from Residential MapTrek, the remaining study procedures will be completed as indicated by the study protocol. The data to be collected at the time of study intervention discontinuation will include the following:

• The reason(s) for discontinuing the participant from the intervention, and methods for determining the need to discontinue

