9.2 SAMPLE SIZE DETERMINATION

To achieve 80% power to detect a 1,750 step difference in step counts between the pre- and post-intervention periods, with a standard deviation of 2,000 steps and a significance level of 0.05, we are required to enroll at least 42 participants. If we add an additional 25% for possible drop outs, we will need to enroll at least 50 participants into the older adult group.

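### Satisfaction is surveyed once, after week 8, with no exit survey or stated denominator for people who leave the study earlier, so reported satisfaction may be too favourable

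*Combined protocol and SAP*

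**What the plan says.** Section 3 fixes the time point for the acceptability objective, "We will assess acceptability at 8 weeks", and justifies it thus: "Participants will have just finished the intervention at 8 weeks". Section 8.1 (Aim 3) splits acceptability in two: "To assess the acceptability of the intervention, we will measure participant adherence and satisfaction".

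- **Satisfaction** comes from the process evaluation: "Process evaluations were administered to participants via phone or in-person during the first week after the active intervention". It asks what people liked, what kept them from playing and what should change. Focus groups follow in the third week of follow-up. The synopsis puts the exit survey at about 10 to 15 minutes.
- **Adherence** needs no survey: "Adherence will be measured by examining the enrollment, completion, and compliance rates". The completion rate is the "number of people who finish the study out of those who enrolled".

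On leaving early, 7.1 keeps a participant who discontinues in the remaining study procedures. The one item it lists for collection at that moment is: "The reason(s) for discontinuing the participant from the intervention, and methods for determining the need to discontinue". Section 7.2 allows withdrawal from the study at any time and lets the investigator remove a participant on several grounds, among them marked non-compliance with the intervention and medical events. Section 7.3 treats a person who cannot be reached as withdrawn. Neither 7.2 nor 7.3 mentions a satisfaction survey on exit.

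Section 9.3 (analysis populations) has a heading and no text. Section 9.4.3 plans descriptive and qualitative analysis of the process evaluation, without a denominator or a rule for missing responses.

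**The concern.** A satisfaction figure taken only from people still in the study at week 8 describes those who stayed, yet it is likely to be read as the view of the older adults who enrolled. Leaving may be related to the opinion being measured. Someone who dislikes the game may quit, and someone who does not engage with it can be removed for non-compliance before anyone asks why. These people are also well placed to answer the survey's own question about barriers, and 8.1 says the answers will shape later MapTrek interventions. What is at stake is the satisfaction and barrier data, not the step-count analysis.

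**Working it through.** **Step 1. Who reaches the survey.** Setting 4.4, 7.1 to 7.3 and 8.1 side by side, for a participant who stops before week 8:

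| Route | Section | Satisfaction survey | Completion rate |
|---|---|---|---|
| Stops the game, stays in the study | 7.1 | Still due, after week 8 | Not a completer under 4.4 |
| Withdraws from the study | 7.2 | None specified | Not a completer |
| Removed by the investigator | 7.2 | None specified | Not a completer |
| Lost to follow-up | 7.3 | None specified; treated as withdrawn | Not a completer |

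The gap is therefore the last three rows, and only the satisfaction column.

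**Step 2. Plan figure to reproduce.** There is none. The documents give no expected satisfaction rate, no expected response rate and no success threshold for acceptability.

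**Step 3. Bounds that need no assumption about leavers' views.** Let d be the fraction of those enrolled who are not surveyed and p the proportion satisfied among respondents. The all-enrolled proportion lies between

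- (1 − d) × p, if nobody unsurveyed was satisfied, and
- (1 − d) × p + d, if everybody unsurveyed was satisfied.

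Inputs:
- p = 0.702. This is the share of participants in the office-worker trial described in 4.2 who called MapTrek fun, borrowed only to set the scale.
- d = 0.25. This is the allowance in 9.2, "If we add an additional 25% for possible drop outs", taken here as if every loss fell before the survey.
- d = 0.16. The headcounts in 9.2 leave room for 50 − 42 = 8 losses, and 8/50 = 0.16.
- d = 0.10. An assumption for a lighter loss.

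| d | Lower | Upper |
|---|---|---|
| 0.25 | 0.75 × 0.702 = 0.5265 (52.6%) | 0.5265 + 0.25 = 0.7765 (77.6%) |
| 0.16 | 0.84 × 0.702 = 0.5897 (59.0%) | 0.5897 + 0.16 = 0.7497 (75.0%) |
| 0.10 | 0.90 × 0.702 = 0.6318 (63.2%) | 0.6318 + 0.10 = 0.7318 (73.2%) |

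The width of each range equals d. In the first row the last digit is dropped.

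**Step 4. Direction.** The error in the respondents-only figure is d × (respondents' rate − non-respondents' rate). At d = 0.25:

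- leavers 40 points less satisfied: 0.25 × 0.40 = +10 points
- leavers 20 points less satisfied: 0.25 × 0.20 = +5 points
- leavers equally satisfied: 0
- leavers 10 points more satisfied: 0.25 × (−0.10) = −2.5 points

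**Step 5. Would dividing by everyone enrolled cure it?** Assume 80% of stayers and 40% of leavers are satisfied, with d = 0.25. The true rate is 0.75 × 0.80 + 0.25 × 0.40 = 0.70. Respondents alone give 80%. Satisfied respondents divided by all enrolled give 0.75 × 0.80 = 60%, an error of the same 10 points in the opposite direction. The denominator alone does not solve the problem.

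**The case against.** A reader might infer that leavers vanish from the acceptability result, that nothing but a reason is ever obtained from someone who stops, and that the result is therefore biased upward. The documents do not support that reading:

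- Acceptability is adherence plus satisfaction, and every early leaver lowers the completion rate. Disengagement also shows in the wear-and-sync compliance rate.
- Section 7.1 keeps people who stop only the game in the remaining procedures, which include the process evaluation. The recorded reason is what is collected at the moment of stopping; it is not the last contact.
- Upward bias is plausible but not established. No satisfaction rate for leavers appears anywhere, and some grounds in 7.2, such as medical events, need have nothing to do with disliking the game.
- The 25% is a sample-size allowance, not a forecast of missing surveys. Completion under 4.4 runs through the 4-week follow-up, so some losses may come after the survey.
- The study is a single-arm pilot, and this outcome is secondary, descriptive and formative. No decision in the documents turns on a satisfaction percentage.

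All of this stands, and it narrows the point. It does not close the gap for people who leave the study itself before the survey. The completion rate shows that they left; it cannot show whether they found the game enjoyable, which features helped or what got in the way, and that is what the process evaluation is for.

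**Conclusion.** The concern holds in a limited form. Followed as written, the plan yields satisfaction and barrier data only from people still in the study when the week-8 survey is given. Those who withdraw, are removed or are lost before then are not covered, and no denominator or missing-data rule makes the gap visible. Reported satisfaction may be too favourable.

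The size and sign cannot be known from the documents. If 25% went unsurveyed, a reported 70.2% would be compatible with 52.6% to 77.6% of all enrolled; at 10% the range is 63.2% to 73.2%. Both ranges rest on a borrowed satisfaction rate and an assumed unsurveyed fraction, and the 25% case assumes that the whole allowance is lost before the survey. This is a cheap improvement to a secondary outcome and does not touch the primary analysis.

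**What to change.** 1. **Section 7.2:** offer the existing process evaluation, by phone or in person, when a participant leaves the study before week 8.
2. **Section 7.1:** offer it also when a participant stops the game, rather than waiting for the week after the active period.
3. **Section 8.1 (Aim 3) and 9.4.3:** report satisfaction among respondents together with the number surveyed out of all enrolled. Show early leavers' answers separately, because they will have taken part in fewer races. Give the best- and worst-case bounds from Step 3 for those not surveyed, and do not count them as dissatisfied.

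The cost is one existing 10 to 15 minute survey given earlier to a small number of people, in a mode already planned, plus a few extra table entries. Some leavers will decline or be unreachable, so the gap shrinks but does not close, and the satisfaction figure may come out lower. Section 8.1 describes the process evaluation in the past tense; if this cohort has already been surveyed, items 1 and 2 may come too late for it, but item 3 can still be applied.

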8.2 SAFETY ASSESSMENTS

N/A

8.3 ADVERSE EVENTS AND SERIOUS ADVERSE EVENTS

8.3.1 DEFINITION OF ADVERSE EVENTS

Adverse event means any untoward medical occurrence associated with the use of the physical activity intervention in humans, whether or not considered intervention-related.

8.3.2 DEFINITION OF SERIOUS ADVERSE EVENTS

An AE or suspected adverse reaction is considered "serious" if, in the view of either the investigator or sponsor, it results in any of the following outcomes: death, a life-threatening adverse event, inpatient hospitalization or prolongation of existing hospitalization, a persistent or significant incapacity or substantial disruption of the ability to conduct normal life functions, or a congenital anomaly/birth defect. Important medical events that may not result in death, be life-threatening, or require hospitalization may be considered serious when, based upon appropriate medical judgment, they may jeopardize the patient or subject and may require medical or surgical intervention to prevent one of the outcomes listed in this definition.

8.3.3 CLASSIFICATION OF AN ADVERSE EVENT

8.3.3.1 SEVERITY OF EVENT

All AEs will be assessed by the team medical director ([name], MD).

8.3.3.2 RELATIONSHIP TO STUDY INTERVENTION/EXPERIMENTAL MANIPULATION

All AEs will have their relationship to study participation assessed with a level of specificity appropriate to the study design. The medical director will determine whether the AE was related (reasonable possibility event was caused by participation) or unrelated (not reasonable possibility) to the participant's study participation.

